18.2 CLINICAL EXAMINATION

The categorical variables to be described are, N and (%):

- Has the bone reached a satisfactory consolidation? (Yes / No / Partially)
- The patient can stand up? (Yes / No (Non-weight-bearing)), if 'Yes':
 - Weight-bearing Protocol (if not prescribed by surgeon, report what is known) (Toe-touch weight-bearing (TTWB) / Partial weight-bearing (PWB)/ Full weight-bearing (FWB))
 - The patient walks? (Yes / No)
- How frequent did the patient reported pain at the affected limb before JTIN application? (Never / Some of the days / About half of the days / Most of the days /Everyday), is not equal to 'Never' VAS Pain Score according to the patient will be described (Mean, SD, Median, Q₁, Q₃, Min, Max)
- Was the pain pharmacologically treated? (Yes / No / unknown)

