19.2 CLINICAL EXAMINATION

The categorical variables to be described are, N and (%):

- Has the bone reached a satisfactory consolidation? (Yes / No / Partially), is not equal to 'Yes' answer this question:
 - Bone consolidation is expected at this visit, please explain why the patient didn't reach bone consolidation
- The patient can stand up? (Yes / No (Non-weight-bearing)), if 'Yes':
 - Weight-bearing Protocol (if not prescribed by surgeon, report what is known) (Toe-touch weight-bearing (TTWB) / Partial weight-bearing (PWB)/ Full weight-bearing (FWB))
 - The patient walks? (Yes / No)
- Calculation double, If 'Calculation double' is equal to '1' answer this question
 - Explain why the patient cannot stand if bone is consolidated
- How frequent did the patient reported pain at the affected limb before JTIN application? (Never / Some of the days / About half of the days / Most of the days /Everyday), is not equal to 'Never' VAS Pain Score according to the patient will be described (Mean, SD, Median, Q₁, Q₃, Min, Max)
- Was the pain pharmacologically treated? (Yes / No / unknown)

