20.2 CLINICAL EXAMINATION

The categorical variables to be described are, N and (%):

- Has the bone maintained a satisfactory consolidation? (Yes / No / Partially), is not equal to 'Yes' answer this question:
 - Bone consolidation is expected at this visit, please explain why the patient didn't reach bone consolidation and if there is any change between previous visit:
- The patient can stand up? (Yes / No (Non-weight-bearing)), if 'Yes':
 - Weight-bearing Protocol (if not prescribed by surgeon, report what is known) (Toe-touch weight-bearing (TTWB) / Partial weight-bearing (PWB)/ Full weight-bearing (FWB)
 - The patient walks? (Yes / No)
- Calculation double, If 'Calculation double' is equal to '1' answer this question
 - Explain why the patient cannot stand if bone is consolidated
- How frequent did the patient reported pain at the affected limb before JTIN application? (Never / Some of the days / About half of the days / Most of the days /Everyday), is not equal to 'Never' VAS Pain Score according to the patient will be described (Mean, SD, Median, Q₁, Q₃, Min, Max)
- Was the pain pharmacologically treated? (Yes / No / unknown)

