21.2 CLINICAL EXAMINATION

The categorical variables to be described are, N and (%):

- Has the bone maintained a satisfactory consolidation? (Yes / No / Partially), is not equal to 'Yes' answer this question:
 - Bone consolidation is expected at this visit, please explain why the patient didn't reach bone consolidation and if there is any change between previous visit:
- The patient can stand up? (Yes / No (Non-weight-bearing)), if 'Yes':
 - Weight-bearing Protocol (if not prescribed by surgeon, report what is known) (Toe-touch weight-bearing (TTWB) / Partial weight-bearing (PWB)/ Full weight-bearing (FWB))
 - The patient walks? (Yes / No)
- Calculation double, If 'Calculation double' is equal to '1' answer this question
 - Explain why the patient cannot stand if bone is consolidated

- How frequent did the patient reported pain at the affected limb before JTIN application? (Never / Some of the days / About half of the days / Most of the days / Everyday), is not equal to 'Never' VAS Pain Score according to the patient will be described (Mean, SD, Median, Q₁, Q₃, Min, Max)
- Was the pain pharmacologically treated? (Yes / No / unknown)
- Was the Gillet Score performed at this visit? (Yes / No) is equal to 'Yes' Gillette Functional Assessment Questionnaire result will be described (Mean, SD, Median, Q₁, Q₃, Min, Max)

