24.2 BONE UNION ACHIEVEMENT

The categorical variables to be described are, N and (%) and Clopper-Pearson confidence intervals will be shown at 95.0% as well, for the overall population and for subgroups of patients defined according to OI Type Diagnosis (Mild/Non-deforming / Severe / Highly Severe/Progressively deforming / Lethal) as defined in section 15.6 of this document:

- Number of procedures that reached a satisfactory bone consolidation in any visit (considering at the first visit in which the answer is “Yes” in “Has the bone reached a satisfactory consolidation?” variables in removal or bone consolidation visits)
- Number of patients that reached a satisfactory bone consolidation in any visit or procedure (considering at the first visit in which the answer is “Yes” in “Has the bone reached a satisfactory consolidation?” variables in removal or bone consolidation visits)

The descriptive statistic (Mean, SD, Median, Q₁, Q₃, Min, Max) will be shown for the following continuous variable, for the overall population and for subgroups of patients defined according to OI Type Diagnosis (Mild/Non-deforming / Severe / Highly Severe/Progressively deforming / Lethal) as defined in section 15.6 of this document:

- Time to full a satisfactory bone consolidation from surgery (months), per procedure, considering at the first visit in which the answer is “Yes” in “Has the bone reached a

satisfactory consolidation?" variables in removal or bone consolidation visits. Calculated as date of first consolidation minus date of surgery.

A list with bone consolidation variables will be shown.

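### SAP 24.2 fixes bone union at the first Yes and has no rule for a later contradicting answer; add an 'achieved and maintained' row beside 'ever achieved'

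*SAP*

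**What the plan says.** At procedure level, SAP 24.2 defines the union outcome as the "Number of procedures that reached a satisfactory bone consolidation in any visit (considering at the first visit in which the answer is" Yes, and limits the source items to the "variables in removal or bone consolidation visits". The patient-level count follows the same rule and is met by any one of the patient's nails: "Number of patients that reached a satisfactory bone consolidation in any visit or procedure". Time to consolidation runs from surgery to that same first Yes.

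The consolidation question is asked four times:
- Plaster removal, about 2 months (SAP 18.2): "Has the bone reached a satisfactory consolidation? (Yes / No / Partially".
- Bone consolidation visit, about 5 months (SAP 19.2): the same question again, with a prompt if the answer is not Yes: "Bone consolidation is expected at this visit, please explain why the patient" did not get there.
- 9 months (SAP 20.2): "Has the bone maintained a satisfactory consolidation? (Yes / No / Partially), is not equal to 'Yes' answer this question", followed by a request to explain.
- 1 year (SAP 21.2): "Has the bone maintained a satisfactory consolidation? (Yes / No / Partially", with the same request.

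The later answers are tabulated by visit, and 24.2 adds a listing of the consolidation variables. None of them can change a success already counted.

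Protocol 12.2.2 asks for the number and proportion of procedures with union achieved, with a 95% interval. It names no deciding visit and no maintenance condition. Protocol 6.2 treats union as the main performance endpoint and plans a visual comparison with other devices. Protocol 12.3 sets it against an 80% literature mean.

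**The concern.** The forms allow an early Yes to be contradicted: the question is repeated at 5 months, and the two later visits ask specifically whether consolidation held. The endpoint does not use those answers. A bone recorded as consolidated at 2 months and as not consolidated at 5 months enters the headline proportion, its interval and the time summary as a union at 2 months.

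The union rate is the figure most likely to be set beside 80% in support of the device's performance. A reader of that figure alone could not tell a union that held from one the investigator later withdrew. One nail could also be recorded as a non-union or delayed-union adverse event under SAP 23 and as a union success under 24.2, with nothing to reconcile the two.

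**Working it through.** **1. The plan's own figures.** The exact (Clopper-Pearson) 95% limits for x of n are: lower = 2.5% quantile of Beta(x, n − x + 1); upper = 97.5% quantile of Beta(x + 1, n − x).
- 15 procedures (protocol 12.3): with x = 0.31 × 15 = 4.65, the upper limit is 59.4%, below the 60% ceiling. With n = 14 it is 60.5%. The 15 reproduces.
- 25 procedures: 20 / (1 − 0.20) = 25. Reproduces.
- 20 procedures for union at 80%: no precision or power criterion is stated, so there is nothing to reproduce. At 16/20 the exact interval is 56.3% to 94.3%.

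None of these depends on the counting rule.

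**2. What the rule does to each answer pattern.** 'Maintained' here uses the consolidation and 1-year visits only.

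| 2 months | 5 months | 1 year | SAP 24.2 | Achieved and maintained |
|---|---|---|---|---|
| Yes | Yes | Yes | united, 2 months | united, 2 months |
| No | Yes | Yes | united, 5 months | united, 5 months |
| Yes | No or Partially | any | united, 2 months | reversed |
| Yes | Yes | No or Partially | united, 2 months | reversed |
| No | Yes | No or Partially | united, 5 months | reversed |
| No | No | any | not united | not united |

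The definitions differ only in the three rows where a Yes is contradicted. In each, 24.2 scores a success. Among procedures with an early Yes, the rule can therefore only raise the rate.

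**3. Size.** The documents give no frequency for reversals, so the number is an assumption, taken here as 0 to 4. Start from 16 of 20 counted at the first Yes. Each reversal is worth 1/20 = 5 percentage points.

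| Reversals | Maintained | Rate | Exact 95% CI |
|---|---|---|---|
| 0 | 16/20 | 80.0% | 56.3 to 94.3 |
| 1 | 15/20 | 75.0% | 50.9 to 91.3 |
| 2 | 14/20 | 70.0% | 45.7 to 88.1 |
| 3 | 13/20 | 65.0% | 40.8 to 84.6 |
| 4 | 12/20 | 60.0% | 36.1 to 80.9 |

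**4. Time to consolidation.** The direction is not fixed. Use nominal visit times and four procedures, one of them reversed:
- Reversed case first Yes at 2 months, the others at 5: (2 + 5 + 5 + 5)/4 = 4.25 months as planned, against 5.0 with the case removed. The plan gives the shorter mean.
- Reversed case first Yes at 5 months, the others at 2: (5 + 2 + 2 + 2)/4 = 2.75 as planned, against 2.0. The plan gives the longer mean.

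**The case against.** The best defence is that 24.2 does what the protocol asks. The endpoint is union achieved. The protocol attaches a 1-year horizon to implant survival and to fracture-free survival but not to union, and the 80% benchmark is also worded in terms of union achieved. Sustained union is a stricter quantity, and replacing the endpoint with it might make the literature comparison less like with like. This stands. It is a reason to keep the 'ever' row and label it, not to leave contradicted answers without a rule.

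Later loss is also not hidden. It appears in the visit tables, in the 24.2 listing, possibly as an adverse event, and in 24.3 when there is a same-bone fracture. That is true, but none of these carries through to the reported proportion, its interval or the time summary. Loss of consolidation without a fracture is outside 24.3.

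The 9-month answer is weaker evidence. Protocol 10.2.6 mentions neither a radiograph nor a consolidation assessment at that visit, and SAP section 20 has no imaging output. The schedule in protocol 4.1, hard to read in the extracted text, seems to mark an X-ray there. A 9-month Partially should not by itself overturn a radiographic Yes.

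Finally, the same clause leaves out unions first reached after the consolidation visit, despite its reference to any visit. That works in the opposite direction, so the net bias of 24.2 is unknown. It concerns different procedures and does not cancel this point.

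**Conclusion.** The gap is real. SAP 24.2 has no rule for an early Yes that is later contradicted, and every such case stays a success. At 20 procedures each is worth 5 points; two would separate 80.0% from 70.0%. The count of reversals is assumed throughout.

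Four stronger readings are tempting and not supported:
- That 2 to 7 of 20 nails are affected. Applying the protocol's 8.47% to 36% range gives 1.7 to 7.2, but that is a literature range for non-union and delayed union. A bone that never unites may be No throughout and is then already scored correctly.
- That time to consolidation is always shortened. Step 4 of the working shows it can go either way.
- That over-calling is likeliest at plaster removal. The protocol states the same criterion (surgeon's judgment plus cortical bridging on radiographs) at 2 months, 5 months and 1 year.
- That the SAP contradicts the protocol and the headline endpoint must be replaced. 'Ever reached' is a legitimate reading; the SAP just does not say it chose it.

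Severity is minor to moderate. Union is a secondary endpoint in a single-arm descriptive study, with no test or pass threshold, and the 15/20/25 figures do not change.

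**What to change.** In SAP 24.2, before the data are analysed:
1. Keep the first-Yes count as the 'achieved' row and label it as ever achieved.
2. Add an 'achieved and maintained' row with its own Clopper-Pearson interval. It counts a Yes not followed by No or Partially at the bone consolidation or 1-year visit, where the protocol plans radiographic assessment. State how many of these have no 1-year answer, since missing data are not imputed.
3. Give time to consolidation under both definitions.
4. List every reversed case with the investigator's explanation. Show 9-month answers in this listing only, unless imaging was available at that visit.
5. Flag reversals that coincide with a same-bone fracture already counted in 24.3, using the sponsor's confirmation list planned there.

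The cost is some SAP wording and one derivation; the consolidation answers are already collected. The sustained rate may come out below the 'ever' rate. Setting both rows in advance avoids choosing the headline after seeing the results.

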7.2 Subjects and Sites Numbers

This study will be conducted only on patients with a regular indication for JTIN as per IFU (no off-label use will be included): the nail is indicated for fractures, osteotomies, malunions and non-unions in femur and tibia in pediatric patients suffering from osteogenesis imperfecta. The JTIN is intended to be used in pediatric patients, older than 18 months.

This study includes only one site (monocentric) located in Paris, France. The site was chosen for this study due to the number of subject devices already implanted, and the wideness of the indications covered by the surgeries. The site was also positively evaluated by sponsor for the appropriate qualification and competency of the investigator and of the staff, and availability of facilities and equipment.

The enrollment objective for this study is of 20 evaluable cases (i.e. procedures, see paragraph "Determination of the Sample Size"). For the purposes of this study, a case is defined as one implanted JTIN nail in one treated bone. Each case can be evaluated and recorded from implantation to the last visit for this study (see "Visits and Assessments Schedule" table and "Procedure" paragraph) or up to implant removal if this happens before the last visit. For each case one eCRF record will be created (see "Subject Identifier" paragraph).

Therefore, a single patient at the clinical site can contribute for more than one case e.g.: a patient can have several JTIN each implanted in a different bone, or can have more JTIN implanted in the same bone but at different times.

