12.3 Determination of the Sample Size

Due to the observational nature of the study, no formal sample size calculation has been done, but a revision of the literature on the complication rates (intended as at least one serious/not serious adverse event certainly or possibly related to the procedure up to 1 year follow-up) has been made. The scientific literature reports that the percentage of procedures which develop at least one serious/not serious adverse event certainly or possibly related to the procedure itself is between 9% and 60%, with a mean of 31%. Assuming a complication rate aligned or better than the mean observed in literature (31%), a sample size of 15 procedures will be sufficient to estimate the adverse event rate with the upper limit of the 95% confidence interval equal or lower than the worst complication rate seen in literature (i.e. 60%).

Starting from this sample size, to also assume that the success rate (intended as proportion of procedures that result in a bone union achieved) is aligned or better than the mean observed in literature (80%), 20 procedures will be needed.

Considering a drop-out or a non-evaluable rate of 20% of the procedures, a total of approximately 25 procedures should be made. Each subject could have from 1 to 4 procedures. Assuming the worst scenario of no more than 1 procedure for subjects, a maximum of 25 subjects needs to be enrolled. Anyway, the enrolment will stop when the total number of the procedures is reached.

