24.4 WEIGHT BEARING GRADE

The categorical variables to be described are, N and (%) and Clopper-Pearson confidence intervals will be shown at 95.0% as well, for the overall population and for subgroups of patients defined according to OI Type Diagnosis (Mild/Non-deforming / Severe / Highly Severe/Progressively deforming / Lethal) as defined in section 15.6 of this document:

- Number of procedures that reached a Full weight-bearing (FWB) from surgery in any visit
- Number of Patients that reached a Full weight-bearing (FWB) from surgery in any visit or procedure

The descriptive statistic (Mean, SD, Median, Q₁, Q₃, Min, Max) will be shown for the following continuous variable, for the overall population and for subgroups of patients defined according to OI Type Diagnosis (Mild/Non-deforming / Severe / Highly Severe/Progressively deforming / Lethal) as defined in section 15.6 of this document:

- Time to Full weight-bearing from surgery (months), per procedure, considered at the first date in which the answer is "Full weight-bearing (FWB)" in "Weight bearing protocol assigned" variables. Calculated as date of the first visit of Full weight-bearing minus date of surgery.

A list with Weight bearing grade variables will be shown.

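### SAP 24.2 scores a child as united if any one enrolled nail consolidates, which hides non-unions in children with discordant nails from the patient-level union rate

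*SAP*

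**What the plan says.** Protocol 7.2 makes the nail the unit: "a case is defined as one implanted JTIN nail in one treated bone". One child "can have several JTIN each implanted in a different bone, or can have more JTIN implanted in the same bone but at different times". Protocol 12.3, repeated in SAP 9, gives the range: "Each subject could have from 1 to 4 procedures". The SAP expects multi-nail children. Section 15.3 tabulates procedures per patient, and the note in 16.1 says that several implants may be placed in one operation.

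Protocol 12.2.2 analyses bone union per procedure only. SAP 24.2 keeps that count, "Number of procedures that reached a satisfactory bone consolidation in any visit", and adds a patient-level count, "Number of patients that reached a satisfactory bone consolidation in any visit or procedure". Both get a Clopper-Pearson 95% interval, overall and by OI severity group. The section also plans a listing: "A list with bone consolidation variables will be shown". No count of children in whom every treated bone united is planned.

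SAP 24.4 uses the same patient-level construction for weight bearing: "Number of Patients that reached a Full weight-bearing (FWB) from surgery in any visit or procedure".

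**The concern.** An at-least-one rule suits a harm. In SAP 23.1 (adverse events) and 24.3 (fractures) it flags a child in whom anything went wrong. Applied to a success it does the opposite: one good nail clears the child, and a non-union elsewhere in that child no longer counts. Because Protocol 7.2 admits repeat nails in one bone, a nail that failed and was replaced can also be masked, if the replacement is enrolled and unites.

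Protocol 6.2 calls union the main performance endpoint and plans a visual comparison of the secondary endpoints with other devices. The 80% reference in Protocol 12.3 is a proportion of procedures. A patient-level percentage that tends to rise with the number of nails per child could be read beside it as better performance. If nail counts differ between OI severity groups, the subgroup percentages would shift for the same reason.

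**Working it through.** **The plan's own figures.** The plan gives no patient-level union rate to reproduce. Its per-procedure figures are 80% union and 20 evaluable procedures, raised to 25 for 20% loss: 20 / (1 − 0.20) = 25, which agrees. The documents give no criterion for the number 20 with respect to union, so that step cannot be re-derived. At 16/20 = 80% the Clopper-Pearson interval is 56.3% to 94.3%.

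**Inputs.** Union per nail p = 0.80 (Protocol 12.3, SAP 9). Nails per child k = 1 to 4 (same sections). The within-child correlation ρ is not in the documents; it is assumed here and varied from 0 to 1. The mix of k is not given either, so results are shown for each k.

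**Formulas.** Independent nails: P(any unite) = 1 − (1 − p)^k and P(all unite) = p^k. Correlated nails: beta-binomial with a = p(1 − ρ)/ρ and b = (1 − p)(1 − ρ)/ρ. P(all fail) is the product over i = 0 to k − 1 of (b + i)/(a + b + i). P(all unite) is the same product with a in the numerator.

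For k = 2 and ρ = 0: any = 1 − 0.2² = 0.96; all = 0.8² = 0.64. For k = 2 the beta-binomial reduces to adding ρp(1 − p) = 0.3 × 0.16 = 0.048 to the chance that both fail and to the chance that both unite. So any = 1 − (0.04 + 0.048) = 0.912 and all = 0.64 + 0.048 = 0.688.

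| Nails per child | Any, ρ = 0 | All, ρ = 0 | Any, ρ = 0.3 | All, ρ = 0.3 | Either rule, ρ = 1 |
|---|---|---|---|---|---|
| 1 | 80% | 80% | 80% | 80% | 80% |
| 2 | 96.0% | 64.0% | 91.2% | 68.8% | 80% |
| 3 | 99.2% | 51.2% | 95.0% | 61.4% | 80% |
| 4 | 99.8% | 41.0% | 96.7% | 56.0% | 80% |

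**Non-unions hidden.** Under independence, the share of non-united nails in children still scored as united is 1 − 0.2^(k − 1): 0% for one nail, 80% for two, 96% for three and 99.2% for four.

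**Worked example.** Ten children have two nails each, and 16 of 20 nails unite.
- The four non-unions fall in four children: any = 10/10 = 100% (69.2% to 100%); all = 6/10 = 60% (26.2% to 87.8%).
- The four non-unions fall in two children: any and all both give 8/10.

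**Direction is not guaranteed.** Child A has four nails, all united, and child B has one nail, not united. Procedures: 4/5 = 80%. Patients under the any rule: 1/2 = 50%.

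**The case against.** The strongest reply is that nothing of consequence depends on this line. The protocol's endpoint is the per-procedure proportion. SAP 24.2 lists it first with its own interval, and the patient-level count is a supplementary description with no test or threshold. That stands, and it limits the point to the patient-level figure.

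A reader might infer that non-unions disappear from the study. They do not. The procedure count and the listing keep them, and SAP 19.2 records why a bone has not consolidated. Non-union is on the anticipated-effects list in Protocol 11.1.5, so a non-union reported as an adverse event would probably also appear by patient under SAP 23.1.1; the CRF is not available to confirm this.

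A reader might also infer that the patient-level rate must exceed the per-procedure rate. The two-child example shows otherwise. Nor do the documents say that the patient-level figure will be compared with 80%, or that children with several nails are more severely affected. Both are possible but unsupported.

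It is also fair that an all-nails rule has the mirror-image fault: it falls from 80% to 41.0% between one and four independent nails at unchanged performance. Replacing one rule by the other is therefore not enough.

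The extension to SAP 24.4 is weaker. Protocol 10.2.4 to 10.2.7 describe weight bearing as assigned to the patient, so nails placed in one operation should often agree, and it is not among the three secondary endpoints in SAP 24.

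None of this alters how the line is scored: a child with a treated bone that did not unite can be reported as a union success, and no planned patient-level union count corrects for it.

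**Conclusion.** The point holds for the patient-level union rate and its interval, overall and by severity group. It does not touch the protocol's per-procedure endpoint, the listing or the sample size.

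With 80% union per nail and two nails per child, the any and all rules differ by 32 percentage points under independence (96% against 64%) and by about 22 at an assumed correlation of 0.3 (91.2% against 68.8%). They do not differ at correlation 1 or with one nail per child. These figures assume the same union probability for every nail, whatever the child's number of nails. On that assumption the patient-level rate is expected to exceed the per-procedure rate, but this is not certain in any one data set. The actual size depends on the mix of nails per child and on within-child correlation, neither of which the documents give. The SAP should be changed, but this is a correction to a supplementary result and not a threat to the study's main conclusions.

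**What to change.** In SAP 24.2:
- Define patient-level union as consolidation of all the child's enrolled evaluable procedures. Say what makes a procedure evaluable, and make clear that a nail exchanged before consolidation counts as not united. Otherwise it could leave the denominator and the masking would return.
- Show children with all, some or none of their nails united, by number of nails per child, because both the any and the all summaries depend on that number.
- Label the per-procedure proportion as the main result and the only one to be set against the per-procedure 80% literature figure.

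In SAP 24.4, apply the same all, some or none display to the patient-level full weight-bearing count, where the effect is probably smaller.

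The cost is a line or two of wording in each section and one more small table. No new data are needed and the sample size is unchanged. The downside is a less favourable patient-level figure wherever nails within a child disagree.
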